4.3. Females of Childbearing Potential and Acceptable Birth Control

Females of childbearing potential must have documentation of a negative pregnancy test at screening and prior to dosing. All female subjects of childbearing potential must agree to abstain from sexual intercourse or to use a highly effective method of birth control during the Study and for at least 7 days after completion of Study drug dosing.

Females are considered to be not of childbearing potential if they have had a total hysterectomy and/or bilateral tubal ligation or hysteroscopic sterilization (documentation for surgeries must be provided before randomization) or are in a postmenopausal state (i.e., females who have had cessation of prior occurring menses for ≥ 24 months without alternative causes or females with premature ovarian failure).

Follicle-stimulating hormone (FSH) will be tested at screening in postmenopausal females only to confirm postmenopausal state.

A highly effective method of birth control is defined as one that results in a low failure rate (i.e., $<1\%$ per year) when used consistently and correctly. Such methods include: combined (estrogen and progestogen containing) hormonal contraception associated with inhibition of ovulation (oral/intravaginal/transdermal); progestogen-only hormonal contraception associated with inhibition of ovulation (oral/injectable/implantable); intrauterine device; intrauterine hormone-releasing system (IUS); bilateral tubal occlusion; vasectomized partner; sexual abstinence. Vasectomized partner is a highly effective birth control method provided that partner is the sole sexual partner of the women of childbearing potential trial participant and that the vasectomized partner has received medical assessment of the surgical success. Sexual abstinence is considered a highly effective method only if defined as refraining from heterosexual intercourse during the entire period of risk associated with the study treatments. The reliability of sexual abstinence needs to be evaluated in relation to the duration of the clinical trial and the preferred and usual lifestyle of the subject. More restrictive methods of birth control may be required as per local country requirements, and this will be defined in the IRB/IEC approved subject informed consent form.

5. STUDY DRUGS

All study drug supplied by the Sponsor must be stored in a secure location accessible only to designated study personnel.

5.1. Description of Study Drugs

5.1.1. TD-1473

[REDACTED]

5.1.2. Placebo

[REDACTED]

5.2. Dosage and Administration

During Induction, subjects will take TD-1473 tablets or placebo once daily for up to 12 weeks. During ATE, subjects will take TD-1473 tablets once daily for up to 48 weeks. For Induction and ATE, subjects will be instructed to take two tablets once daily at approximately the same time each morning before eating and to refrain from eating or drinking anything other than water and non-study medications for at least 30 minutes after dosing.

The Study drug will be taken orally and must be swallowed whole with liquid and not chewed, divided, dissolved, or crushed. If the subject dose is missed in the morning, it can still be taken up to 12 hours after the subject's nominal dosing time, as long as the subject has fasted for at least 4 hours before. After 12 hours post-nominal dosing time, the dose of Study drug should be skipped for that day and the subject should be instructed to take the Study drug on the following day before the first meal of the day.

[REDACTED]

5.4. Drug Accountability and Reconciliation

The investigator or designee is responsible for maintaining accountability records for all study drug(s) received from the Sponsor, in accordance with applicable government regulations and study procedures. The accountability record for study medication (TD-1473 and placebo) will be maintained in a secure location, accessible only to authorized staff members. Details of receipt, distribution or dispensing, and destruction of the material(s) will be recorded in the study medication accountability record according to the clinical site's standard operating procedures. Subjects will be instructed to return all used and unused study medication at each study visit.

Unused and expired study drugs will be disposed of in accordance with written instructions from the Sponsor. Copies of the study medication accountability records will be provided to the Sponsor at completion of the study and will be made available for review by the site monitor during the course of the study.

6. STUDY PROCEDURES

Study procedures will be performed only after written informed consent is obtained. The Screening visits (i.e., Stage 1 and Stage 2) will be performed within 35 days before dosing. One repeat Screening Stage 1 visit is allowed for each subject per the investigator's discretion. No more than one repeat Screening Stage 1 visit or repeat visit-specific procedure/assessment is allowed for each subject, unless prior written approval has been provided by the Sponsor. If the subject does not begin Induction treatment within this 35-day window, Screening evaluation procedures (i.e., Stage 1 and Stage 2) must be repeated. Subjects may be considered for re-screening of both Screening Stage 1 and Screening Stage 2 procedures, depending on the reason for the initial screening failure, per consultation with and approval from the Sponsor.

During the study, every effort should be made to perform study procedures as listed in the Schedule of Study Procedures (Table 1). Assessments will be made and biological samples will be taken in the following recommended order at those study visits at which they coincide: fecal sample collection, adverse event assessment, ECG, vital signs, [REDACTED] clinical laboratory safety samples, [REDACTED] and ileocolonoscopy with biopsies (although ileocolonoscopy should be done within 3 days prior to the Week 12 clinic visit). Study drug administration will be in-clinic on Day 1, Week 4, Week 8, Week 12, ATE Week 16, ATE Week 24, ATE Week 36, and ATE Week 48 after all pre-dose assessments [REDACTED] and procedures have been completed.

Throughout the study, the acceptable window for scheduled assessments is as follows:

- - 3 to + 5 days from the nominal visit date for Week 4, Week 8, ATE Week 4, ATE Week 8, ATE Week 16, ATE Week 24, ATE Week 36, ATE Week 48 and the EOS visits
- -1 to +3 days from the nominal Week 12 clinic visit for the Week 12 ileocolonoscopy with biopsies. The Week 12 ileocolonoscopy and biopsies should be performed on the same day as the Week 12 visit, preferably in the early morning, to permit morning dosing with study drug. However, if not feasible to perform both the ileocolonoscopy and the clinic visit on the same day, the ileocolonoscopy could be performed within 3 days after the Week 12 clinic visit. However, the Week 12 endoscopy must be performed at least 1 day prior to ATE Day 1.
- + 3 days from the nominal visit date for the Week 12 clinic visit
- 1-7 days after the Week 12 clinic visit for ATE Day 1. The Week 12 endoscopy must be conducted at least 1 day prior to ATE Day 1.
- Within 5 days following last dose of study drug for Early IP Discontinuation visit (during Induction or ATE)
- [REDACTED]
- [REDACTED]
- Screening CDAI score is to be obtained prior to starting the bowel preparation for ileocolonoscopy (to assess eligibility criteria).

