- I. Study drug administration will be in clinic on Day 1, Week 4, Week 8, Week 12, ATE Day 1, ATE Week 4, ATE Week 8, ATE Week 16, ATE Week 24, ATE Week 36, and ATE Week 48 on an empty stomach from the night before after all pre-dose assessments [REDACTED] and procedures have been completed. Subject will take the study drug at home for the rest of the study. The last dose of Induction study drug will be taken at the Week 12 clinic visit. No new study drug will be dispensed between the Week 12 clinic visit and ATE Day 1.
- J. Subjects will be provided with an electronic diary (or paper diary if electronic diary is not available) at the Screening Stage 1 visit and instructed on daily diary completion, including symptom monitoring and study drug dosing details. Diaries of symptoms will be collected daily from the Screening Stage 1 visit through the EOS visit. Study drug dosing details will be entered from Day 1 (Induction) through ATE Week 48 (or the last dose of study drug, if the subject prematurely withdraws from study drug). Diary completion will be monitored for completeness at each return study visit after the electronic diary is dispensed (i.e., Screening Stage 2 through the EOS visit). Subjects will be counseled on missed study drug doses and missed diary entries.
- K. Corticosteroid taper, for those that are on corticosteroid at Screening Stage 1, should be initiated at the Week 8 visit. This taper will continue through ATE, as outlined in Section 6.4.30.
- L. Site personnel to call subjects approximately 2 weeks prior to Week 12 visit for reminder of compliance of diary completion. The site will also review compliance on corticosteroid taper (as applicable), review upcoming schedule for Week 12 and the reminders in preparation for the visit.
- M. AE assessments are to include collection and reporting of AEs, SAEs, and AEs of Special Interest (AESIs). Please refer to protocol Section 7 for further details.
- N. Urine beta human chorionic gonadotropin (b-hCG) testing will be performed before dosing when dosing in-clinic and anytime during all other visits for females of childbearing potential to confirm absence of pregnancy. If urine b-hCG test is positive, confirm with serum b-hCG test.
- O. Required for postmenopausal females.

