6.3.6. Week 12 (Induction)

Subjects should be instructed to fast from food and non-clear fluids on the evening prior to the Week 12 visit to ensure a minimum 8-hour fast prior to the fasted blood sample collection.

The Week 12 ileocolonoscopy and biopsies should be performed on the same day as the Week 12 visit, preferably in the early morning, to permit morning dosing with study drug. However, if not feasible to perform both the ileocolonoscopy and the clinic visit on the same day, the ileocolonoscopy could be performed anytime within 3 days after the Week 12 clinic visit. If the study activities of this Week 12 visit are to be completed over two different visits, the study drug should be continued until the later of the two visits.

The following procedures will be performed at the Week 12 visit:

- Tobacco use status
- Vital signs
 - Heart rate (HR) and systolic and diastolic blood pressure (BP)
 - Respiratory rate
 - Body Temperature
- 12-lead ECG
- Physical examination is to be conducted according to local practice
- Weight
- Blood collection
 - Hematology
 - Serum chemistry
 - Overnight fasting lipid panel
 - [REDACTED]
 - [REDACTED]
 - [REDACTED]
 - [REDACTED]
 - [REDACTED]
 - [REDACTED]
 - [REDACTED]

- Urine collection
 - Urinalysis
 - Pregnancy test for females of childbearing potential – If urine b-hCG test is positive, confirmation with serum b-hCG test is required
- Fecal collection [may be collected within 3 full days (approximately 72 hours) prior to the visit but must precede the start of a bowel preparation if it is to be collected during the same day as the bowel preparation; however, it is preferable that the stool sample be collected during the first bowel movement in the morning]
 - [REDACTED]
- Ileocolonoscopy and Biopsies (Refer to Section 6.4.18)
- Disease Assessments
 - CDAI Components
 - Abdominal Pain and Total Stool Frequency Scores
 - SES-CD Score
 - [REDACTED]
 - [REDACTED]
- Perform drug accountability and review subject's compliance with study drug dosing
- Subject dosing in clinic (in the morning before eating; last dose of Induction study drug)
- Review concomitant medications
- Continue corticosteroid taper by 2.5 mg per week (Section 6.4.30), for subjects who entered the study on corticosteroids (as applicable)
- Adverse event assessment (AEs, SAEs, Adverse Events of Special Interest)
- Review diary completion and compliance; counsel subject as needed

6.3.7. ATE Day 1

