6.4.25.2. CDAI

The CDAI score is generated using regression coefficients for eight different predictors of disease activity: severity of abdominal pain, general well-being, very soft/liquid stool frequency, extra-intestinal symptoms, need for antidiarrheal drugs, presence of an abdominal mass, body weight and hematocrit. The subject will be provided the Bristol Stool Form Scale as a reference for what to consider very soft/liquid stool. See [Appendix 6](#) for the questions that will be asked on a daily basis to calculate the CDAI. The subscores of abdominal pain (0-3), general well-being, and number of very soft or liquid stools are then summed over the 7 days prior to each visit.

CDAI scores should be calculated using the closest previous 7 days not impacted by the colonoscopy and/or its preparation. Note that symptoms on the day prior, the day of, and the day following a colonoscopy should not be counted as part of the 7 days to avoid effect of the bowel preparation or the procedure on symptoms. Additionally, the remaining predictors are also noted and weighted to create the total CDAI score. See [Appendix 6](#) for the CDAI calculation.¹² Benchmarks for disease activity as measured by the CDAI are: <150, clinical remission; 150 to 219, mildly active disease; 220-450, moderately active disease; and >450, very severe disease. CDAI data will be collected as specified in the Schedule of Study Procedures ([Table 1](#)). Subjects will enter the 4 subjective parameters daily from Screening Stage 1 to the last day of study participation.

[REDACTED]

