3.3.2. CDAI Score

CDAI score is calculated as sum of a Subscore x Multiplier from Appendix 5.2. The following subscores are calculated based on the most recent evaluable 7 days.

- Number of liquid or very soft stools subscore
- Average Abdominal pain subscore
- General well-being subscore

Evaluable days are defined as any non-missing diary days during the 10 days prior to the study visit. The day prior to endoscopy, day of endoscopy and the day following endoscopy will be treated as non-evaluable and treated as missing.

If fewer than 5 evaluable days data are available for any of the above subscores then the subscore is set to missing for that timepoint. If only 5 or 6 evaluable days' data are available for the above mentioned subscores then the subscore total is calculated as:

(Total score over available days/Number of available days)*7

The weight component of the CDAI will be based on ideal weight (see Section 5.3.1.4).

The CDAI score should be calculated for a visit only if ≥ 4 subscores are available at a visit, with missing subscores imputed by carrying forward the last non-missing subscore. If <4 subscores are available at a visit then the CDAI score will be set to missing.

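### Week 12 ileocolonoscopy timing is stated in conflicting ways, and under the SAP's 10-day diary look-back the timing changes how many missed diary entries the primary CDAI can absorb

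*Protocol*

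**What the plan says.** **Endoscopy timing.** Protocol section 6 contains three statements.

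- The recommended order of assessments adds in brackets: "although ileocolonoscopy should be done within 3 days prior to the Week 12 clinic visit".
- The list of visit windows reads, after a minus sign, "1 to +3 days from the nominal Week 12 clinic visit for the Week 12 ileocolonoscopy with biopsies".
- The same bullet continues: "The Week 12 ileocolonoscopy and biopsies should be performed on the same day as the Week 12 visit". If that is not feasible, it allows the procedure up to 3 days after the visit.

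Only the third statement is repeated elsewhere. Protocol 6.3.6 says "the ileocolonoscopy could be performed anytime within 3 days after the Week 12 clinic visit" when the same day is not feasible. Protocol 6.4.18 and footnote C of the SAP schedule (SAP 1.4) agree with it.

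**Last Induction dose.** Protocol Table 1, footnote I, says: "The last dose of Induction study drug will be taken at the Week 12 clinic visit". Footnote I of the SAP schedule says the same. Protocol 6.3.6 and SAP footnote C say that if the Week 12 activities are spread over two visits, "the study drug should be continued until the later of the two visits". SAP 3.7.1 ends induction exposure at the Week 12 visit dose for anyone who reaches that visit.

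**Diary days for the CDAI.** Protocol 6.4.25.2 says: "CDAI scores should be calculated using the closest previous 7 days not impacted by the colonoscopy and/or its preparation". SAP 3.3.2 adds a fixed limit: "Evaluable days are defined as any non-missing diary days during the 10 days prior to the study visit". It treats the day before, the day of and the day after endoscopy as missing. It needs at least 5 evaluable days for each of the three diary subscores. If at least 4 subscores are available at the visit, missing ones are filled with the last non-missing value.

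**The concern.** Sites cannot follow every timing sentence at once. If the clinic visit falls on its nominal date, an endoscopy 2 or 3 days earlier satisfies the bracketed sentence but breaches both the window and the same-day-or-after rule.

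This reaches the primary endpoint because the SAP removes the endoscopy days from a look-back of fixed length. An endoscopy before the visit takes more days out of that window than one on the day, and one after the visit takes none. A subject with too few remaining entries does not get a missing CDAI. The three diary subscores are carried forward, normally from Week 8, into a score labelled Week 12. For subjects on corticosteroids at entry, Week 8 diary data predate the taper that starts at that visit. The primary model then treats the score as observed. SAP 3.3.6.6 tabulates missing subscores at Week 12, but neither sensitivity analysis in SAP 3.3.5 sets the carried-forward ones aside.

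The last-dose wording affects the induction exposure figures. Doses taken between the clinic visit and a later endoscopy, up to 3 days, fall outside the duration in SAP 3.7.1. The drug supply for them is also unclear: Protocol 5.4 has subjects return all medication at each visit, and footnote I says no new drug is dispensed between the Week 12 clinic visit and ATE Day 1.

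**Working it through.** **Inputs.** From SAP 3.3.2: look-back of 10 days before the visit (days −10 to −1); 3 days excluded around endoscopy; minimum of 5 evaluable days. From Protocol section 6: possible endoscopy days −3 to +3. The documents give no daily diary completion rate, so that is an assumption shown as a range. The plan states no figure for this point to reproduce.

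**Step 1: candidate days.** Candidate days = 10 minus the excluded days that fall within −10 to −1. Missed entries tolerated = candidate days − 5.

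| Endoscopy day relative to visit | Excluded days inside the window | Candidate days | Missed entries tolerated |
|---|---|---|---|
| −3 | −4, −3, −2 | 7 | 2 |
| −2 | −3, −2, −1 | 7 | 2 |
| −1 | −2, −1 | 8 | 3 |
| 0 (same day) | −1 | 9 | 4 |
| +1 to +3 | none | 10 | 5 |

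At most 3 days can be removed, so the count cannot fall below 10 − 3 = 7. Counting the visit day inside the 10 days shifts some rows but leaves the minimum at 7.

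**Step 2: chance of a shortfall.** With independent daily completion probability c and k candidate days, the chance of fewer than 5 entries is P(X ≤ 4), X ~ Binomial(k, c). For k = 7 and c = 0.80:

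1 − [21 × 0.8⁵ × 0.2² + 7 × 0.8⁶ × 0.2 + 0.8⁷] = 1 − (0.2753 + 0.3670 + 0.2097) = 0.148.

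| Assumed daily completion | 7 days | 8 days | 9 days | 10 days |
|---|---|---|---|---|
| 95% | 0.4% | <0.1% | <0.1% | <0.1% |
| 90% | 2.6% | 0.5% | 0.1% | <0.1% |
| 80% | 14.8% | 5.6% | 2.0% | 0.6% |

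**Step 3: what a shortfall does.** The CDAI has 8 subscores, 3 of them from the diary. If all three fail and the other five are present, 8 − 3 = 5 ≥ 4, so a score is still calculated, with the diary subscores carried forward.

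**The case against.** The strongest reply is that the SAP window already allows for endoscopy. Ten days is 7 diary days plus 3 excluded days, so with a complete diary it yields the seven unaffected days that Protocol 6.4.25.2 asks for, whatever the timing. That stands. A reader might infer that endoscopy before the visit by itself leaves too few days, or that the primary CDAI then goes missing. The documents support neither: timing alone leaves at least 7 days against a minimum of 5, and a shortfall leads to carry-forward when enough other subscores are present.

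It is also fair that the probabilities rest on assumed completion rates and independent days, and apply only if endoscopy is at least 2 days before the visit. The instruction repeated across sections does not direct that. The plan supports completion with diary review at visits and a Week 10 reminder call. These points limit the size of the effect but do not remove the dependence on timing.

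A reader might also take the last-dose sentences as a flat contradiction. They can be read together: the clinic visit is the default and the split visit is a stated exception. What remains is that footnote I and SAP 3.7.1 do not mention the exception.

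Finally, extending the look-back trades recency for completeness, which is a matter of judgement.

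**Conclusion.** The inconsistency in endoscopy timing within Protocol section 6 is real and sits in current operative text. The last-dose wording is a softer problem: an exception that one footnote and the exposure definition do not carry.

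For the primary CDAI the effect is a loss of tolerance, from 4 missed entries with same-day endoscopy to 2 when it is 2 or 3 days before the visit. It is negligible at 95% daily completion and becomes material only if completion is near 80% and early endoscopy is common. The documents give neither quantity.

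A reader might infer bias between arms. Nothing shows it: treatment is blinded and no link between endoscopy timing and assignment is described. The issue is older diary data entering some Week 12 scores, possibly unevenly across sites. Severity: minor.

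**What to change.** 1. Reconcile the endoscopy-timing statements in Protocol sections 6, 6.3.6 and 6.4.18 and the SAP schedule so that one rule is stated once. The clinical team decides which applies.
2. Reconcile the last-dose statements in Protocol Table 1 footnote I, Protocol 6.3.6, SAP schedule footnotes C and I, and SAP 3.7.1 in the same way, so that the exposure end date follows whichever rule the clinical team confirms.
3. In SAP 3.3.2, count the 10-day look-back in days not excluded for endoscopy. Every subject then has 10 candidate days regardless of endoscopy date. The assumed shortfall at 80% completion becomes 0.6% throughout, and the rule sits closer to Protocol 6.4.25.2.

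The cost is a protocol clarification, a matching edit in SAP 3.7.1 and the SAP schedule, and one sentence in SAP 3.3.2. The downside is that the look-back may reach up to 3 days earlier, to day −13 at most.

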6.1. Schedule of Study Procedures

The schedule of study procedures is summarized in [Table 1](#).

Additional safety tests, such as vital signs (blood pressure [BP], heart rate, respiratory rate, and body temperature), physical exams, ECGs, and laboratory safety tests, may be obtained during the course of the study on the basis of newly available data to ensure appropriate safety monitoring.

6.2. Total Blood Volume

The total estimated volume of blood to be drawn from each subject for safety laboratory assessments, serology panel, lipid panel, serum pregnancy test (if applicable), FSH (if applicable), [REDACTED], QuantiFERON[®]-TB Gold test, [REDACTED], and genetic testing (if applicable) is [REDACTED]. For subjects who consent to the optional genetic testing, [REDACTED]. Additional samples may be drawn for safety laboratory testing as considered necessary by the investigator.

